9.1.2.1 Treatment Period

During Visit 2, the following assessments will be completed before the subject receives their first dose of study drug: MMSE, CDR, ADAS-cog14, FAQ, and NPI-10. (revised per Amendment 01) These assessments will provide baseline measurements for the study. For any given subject, every effort should be made to ensure that the CDR rater remains unchanged throughout the study. (revised per Amendment 04) Inclusion and exclusion criteria will be reviewed again together with concomitant medications and assessment of AEs. A single 12-lead ECG will be conducted. All ECG recordings will be evaluated by a central reader. (revised per Amendment 01) The C-SSRS will also be administered. A baseline routine physical examination with dermatologic review, vital signs measurements, clinical laboratory testing (including viral characterization), urinalysis using urine dipstick, and a urine pregnancy test (females of child-bearing potential only), will be performed. Additional blood samples will be taken for PD/exploratory biomarkers and immunologic assessments. (revised per Amendment 04) Some of the immunologic assessment blood sample will be used to prepare isolated PBMCs which will be stored for testing as required. (revised per Amendment 03) The results of some of the immunologic assessments will be provided to the DSMB for periodic review during the Core Study. (revised per Amendments 01 and 06) Whilst there is no prescribed order in which the assessments at each visit are to be performed, the subject component of the cognitive, functional and quality of life assessments are to be performed in the morning whenever possible, or consistently at the same time of the day and ideally should be completed before the more invasive procedures (eg, physical examination, ECG, blood draw).

Subjects will be randomized at Visit 2 (Day 1) to receive elenbecestat 50 mg per day or placebo administered orally QD in the morning with or without food. Subjects will be encouraged to stay at the site for observation for at least 30 minutes following their first dose of study drug. The duration of this observation period can be extended at the investigator's discretion, eg, if warranted by medical history or concomitant medication. (revised per Amendment 04) Double-blinding to study drug will be in effect throughout the Treatment Period.

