9.5.1.5.6 ELECTROCARDIOGRAMS

Electrocardiograms will be obtained as designated in [Table 4](#) and [Table 5](#). A single 12-lead ECG will be recorded after subjects have been resting in the supine position for at least 5 minutes. If the QTcF machine read is greater than 440 ms on the first single 12-lead ECG, 2 additional 12-lead ECGs will be performed 1 minute apart and the mean of the 3 QTcF values will be calculated. All ECG recordings will be evaluated by a central reader. (revised per Amendments 01 and 06)

On any study day when ECG, vital signs, and blood samples are taken, it is recommended that these procedures should be conducted in the following order: ECG first, followed by vital signs, and then blood samples.

An ECG abnormality may meet the criteria of an AE as described in this protocol (see [Section 9.5.1.5.1](#)) and the CRF Completion Guidelines. In these instances, the AE corresponding to the ECG abnormality will be recorded on the AEs eCRF.

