1. Subjects who complete the 24-month Treatment Period and the 3-month Follow-up Period (Visit 15) of the Core Study, and whose Visit 15 falls within a 4-week window from the start of the Extension Phase. Subjects who discontinue study drug early are not considered to have ‘completed’ the Core Study.
2. Provide written informed consent. Subjects must, in the investigator’s judgment, have the capacity to consent (capacity to consent should be determined in accordance with applicable professional standards and local laws/regulations).
3. Subjects must continue to have an identified study partner who is willing and able to provide follow-up information on the subject throughout the course of the Extension Phase.

Study Design and Plan

The Extension Phase allows eligible subjects to receive elenbecestat 50 mg for up to 24 months (2 years), or until commercial availability of elenbecestat or a lack of positive benefit-risk is determined, whichever comes first.

Subjects who are enrolled and complete the Core Study, including the 3-month Follow-up Period, will have the option to participate in the Extension Phase. Subjects who discontinue from study drug during the Core Study are not eligible to participate in the Extension Phase.

Eligible subjects may enter the Extension Phase immediately following the completion of Visit 15 of the Core Study. Subjects who are eligible to participate in the Extension Phase but who do not provide consent to transition to the Extension Phase on the day of Visit 15 may enter the Extension Phase any time within 4 weeks of Visit 15. For all subjects, assessments performed at Visit 15 will serve as baseline values for the Extension Phase.

Subjects may discontinue from the open-label study drug for any reason but are required to complete the Early Discontinuation (ED) Visit (within 7 days of last dose). In addition, subjects are required to discontinue the open-label study drug if any of the criteria specified in [Section 9.3.3](#) (Removal of Subjects from Therapy or Assessment) are met.

Subjects who complete the 24 months of Extension Phase treatment, or discontinue the study drug are required to complete the Follow-up Visit, 1 month after their last dose. The study will end when the last subject has completed the last Extension Phase study visit.

Treatment

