Elenbecestat will be supplied by the sponsor as tablets of 50-mg dose strength in bottles of 35 tablets. Each subject will receive 1 tablet of 50 mg elenbecestat, to be administered orally QD in the morning with or without food.

Assessments

Assessments will be conducted as shown in [Table 5](#) Visit 15 (Day 1 of the Extension Phase) and as shown in [Table 9](#), for all other Extension Phase visits following the guidelines as indicated for the Core Study in [Section 9.5](#). Concomitant therapy is allowed as stated in [Section 9.4.7](#) and treatment compliance and accountability will be performed as indicated in [Section 9.4.8](#), and [Section 9.4.9](#), respectively.

Safety assessments (physical examinations, neurological examinations, vital signs, safety laboratory tests, ECGs [no central reading of ECGs], signals of potential abuse, pregnancy test for females of child-bearing potential, Columbia Suicide Severity Rating Scale (C-SSRS), and assessment of suicidal thinking/behavior, immunological assessments, safety magnetic resonance imaging (MRI) will be monitored according to [Table 9](#) and all adverse events (AEs) and serious adverse events (SAEs) recorded.

A full neurologic examination will be performed at the start of the Extension Phase (during Visit 15, the last visit of the Core Study), and at Visit 24/ED, but will be abbreviated for all other timepoints.

Safety laboratory blood tests will be collected as indicated in [Table 9](#) and analyzed by a central laboratory.

Blood samples for pharmacodynamic (PD) and biomarker analyses ([Table 7](#)) will be collected as indicated in [Table 9](#). The blood sample for PD analyses should be collected at fasting or at least 2 hours after the most recent meal.

Subjects that have consented to the optional CSF substudy (either at the start of the Core Study or Extension Phase) will have samples taken as indicated in the Table of Assessments to analyze PD and biomarkers ([Table 7](#)). Longitudinal CSF sample is taken before other Visit 24 assessments and whilst subject is still on study drug; for ED, CSF should be taken and no longer than 7 days after the last dose.

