Safety analysis will be performed similarly to analyses in the Core Study. The Core Study baseline will be used for subjects who are randomized to elenbecestat initially, the Extension Phase baseline will be used for subjects who are randomized to placebo but receive elenbecestat during the Extension Phase. The incidence of AEs (including changes from baseline in physical and neurological examinations, and dermatological assessments), out-of-normal-range laboratory safety test variables, abnormal ECG findings, out-of-range vital signs, suicidality (C-SSRS), and changes from baseline in laboratory safety test variables, ECGs, safety MRI, vital sign measurements will be summarized by using descriptive statistics.

Efficacy Analyses

The following efficacy endpoints will be summarized by descriptive statistics and graphs:

- Changes from baseline in CDR-SB, ADCOMS, MMSE, FAQ, ADAS-cog14, and ADAS-cog14 Word List (immediate recall and delayed recall)
- Time to conversion to dementia for subjects who were not clinically staged as dementia at Core Study baseline based on clinical diagnosis
- Change from baseline in NPI-10 and NPI-12
- Proportion of subjects who receive increase and/or initiation of other AD pharmacotherapies

A delayed-start analysis ([Liu-Seifert et al., 2015](#)) will be performed for each efficacy endpoint at various scheduled visits in the Extension Phase. In addition, a mixed effects model for repeated measures (MMRM) will be used to analyze the above endpoints where appropriate.

Biomarker Analyses

The following biomarker endpoints will be summarized by descriptive statistics and graphs:

- Change from baseline in amyloid PET standardized uptake value ratio (SUVR)
- Change from baseline in tau PET signal
- Change from baseline in total hippocampal volume as measured by vMRI
- Change from baseline in the preservation of connectivity as measured by fMRI
- Change from baseline in t-tau, p-tau, A β (1-42) and A β (1-x) in CSF
- Change from baseline A β (1-x) in plasma
- Change from baseline in exploratory biomarkers eg, NFL, VILIP1, YKL-40, and Ng in CSF and plasma

A delayed-start analysis and MMRM model will be used to analyze these biomarker endpoints.

The relationship between efficacy endpoints and biomarker endpoints will be explored using correlation analysis.

Sample Size Rationale

Not applicable.

Table 9 Schedule of Procedures/Assessments in Extension Phase

Phase	Extension												

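### Extension ECG changes are measured from centrally read Core baselines although Extension ECGs are not centrally read, so reading method is confounded with change on drug

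*Protocol*

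**What the plan says.** **Core Study.** Section 9.5.1.5.6 states: "All ECG recordings will be evaluated by a central reader". Section 9.1.2.1 says the same for Visit 2: "A single 12-lead ECG will be conducted. All ECG recordings will be evaluated by a central reader". Table 5, footnote e, has the Visit 15 ECG done for subjects who continue into the Extension.

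**Extension Phase.** Appendix 5 first sends Extension assessments back to the Core rules, "following the guidelines as indicated for the Core Study in" Section 9.5. In the next paragraph it lists "safety laboratory tests, ECGs [no central reading of ECGs], signals of potential abuse", to be monitored according to Table 9. The Table 9 visits start at Visit 16.

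**Baselines.** Appendix 5, Study Design and Plan: "For all subjects, assessments performed at Visit 15 will serve as baseline values for the Extension Phase". Appendix 5, Safety Analyses: "The Core Study baseline will be used for subjects who are randomized to elenbecestat initially, the Extension Phase baseline will be used for subjects" first randomised to placebo.

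**Analysis.** Appendix 5, Safety Analyses, provides that "changes from baseline in laboratory safety test variables, ECGs, safety MRI, vital sign measurements will be summarized" with descriptive statistics. ECG is one of nine items in the Extension primary (safety) endpoint. Section 9.1 confirms that everyone who enters the Extension receives elenbecestat.

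**The concern.** A change from baseline is interpretable when both values come from the same measuring process. Here the process changes at the boundary between the phases, and the analysis subtracts across that boundary. If site and central QTcF readings differ on average, the difference appears as an ECG change during open-label treatment, or it masks a real one. A randomised control arm would carry the same difference and cancel it, but the Extension has none.

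Long-term safety is the primary objective of the Extension, and QTcF has been followed throughout the programme. The thorough QT study described in the clinical safety background found a small but statistically significant concentration-QTc relationship, while excluding an effect above 10 ms at single doses up to 200 mg. An avoidable shift of a few milliseconds would therefore be awkward to interpret. ECG also stands apart here: Appendix 5 keeps laboratory tests, MRI and PET central.

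**Working it through.** The protocol states no figure for this point, so there is none to reproduce. The check traces reading method through the analysis.

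| Value | Visit | Reading method | Source |
|---|---|---|---|
| Baseline, first on elenbecestat | Core baseline (Visit 2) | Central | 9.1.2.1, 9.5.1.5.6 |
| Baseline, former placebo | Visit 15 | Central on the natural reading | 9.5.1.5.6; Table 5 footnote e; Appendix 5 |
| Extension values | Table 9 visits, Visit 16 onward | Not central | Appendix 5, Assessments |

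Visit 15 is both the last Core day and Day 1 of the Extension. It runs under Table 5, and the bracket removing central reading is attached to Table 9, so central reading is the natural inference, though it is not stated outright. If Visit 15 were read at the site, former placebo subjects would have a same-method comparison, while subjects first on elenbecestat would still be compared with a central Visit 2 value. The two groups would then be on different footings.

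**Effect on the mean.** Let b be the average site reading minus the average central reading of the same tracing. Then

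reported mean change = true mean change + b.

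With a true change of 0 ms and assumed b of -5, 0, +3, +5 or +10 ms, the reported mean change is -5, 0, +3, +5 or +10 ms. Without a concurrent control, b cannot be estimated from the planned data. In the Core comparison all readings are central in both arms, so b does not arise.

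**Effect on an absolute category.** Assume, for illustration only, normally distributed QTcF with centrally read mean 420 ms. The share above 450 ms is 1 - Φ((450 - 420 - b)/SD).

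| b (ms) | SD 15 | SD 20 |
|---|---|---|
| -5 | 1 - Φ(2.33) = 1.0% | 1 - Φ(1.75) = 4.0% |
| 0 | 2.3% | 6.7% |
| +3 | 3.6% | 8.9% |
| +5 | 4.8% | 10.6% |
| +10 | 9.1% | 15.9% |

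**Effect on the protocol's own QTc adverse event rule.** Section 9.5.1.5.1 requires QTc above 450 ms together with an increase above 60 ms. Assume no true change, within-subject SD 12 ms and extra reading SD 8 ms. The total SD is √(144 + 64) = 14.4 ms. For b = +10, P(increase > 60) = P(Z > 50/14.4 = 3.47), about 0.03%. For b = +5 it is about 0.007%. The added 450 ms condition can only lower these, so under these assumptions the rule is hardly touched.

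The offsets, the mean and the SDs are all assumptions. The protocol gives none of them.

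**A second method difference.** The repeat-ECG trigger is a machine read above 440 ms in Section 9.5.1.5.6 and Table 5 footnote i, but above 450 ms in Table 9 footnote f. A first machine read between the two is averaged over three tracings in one phase and stands as a single value in the other.

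**The case against.** The strongest reply is that confounding is shown but bias is not. That stands: the size and sign of any difference are unknown, and zero is possible. A reader might infer an offset of about 10 ms from the 440 ms machine-read trigger beside the 450 ms central exclusion limit in exclusion criterion 14. The documents do not support this. The 440 ms figure decides when to repeat a tracing and is not a measured machine-minus-central difference, and Table 9 applies 450 ms to the machine read itself.

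A reader might also infer a surge of outliers, for example with a 30 ms change cut-off. That cut-off is not in the protocol, and the rule that is there is barely affected, as shown above.

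Further, the Extension summaries are descriptive, with no test or decision rule. Ageing and permitted changes in co-medication already prevent attributing an uncontrolled mean ECG change to drug. The placebo-controlled, centrally read Core supplies the main ECG comparison. All of this stands and lowers the severity, but it does not justify adding a confounder that can be removed.

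The choice of which QTcF value enters a table could be left to the SAP. However, the protocol itself fixes both the loss of central reading and the baseline visits without saying how they fit together, so this is more than an omitted detail.

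Finally, a stored site reading at Visit 2 is not assured. The machine-read wording in Section 9.5.1.5.6 is marked as revised by Amendment 06, and the preceding protocol text speaks only of QTcF. This also stands and shapes the fix.

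**Conclusion.** The point holds in a limited form. As written, the plan compares non-central Extension ECG readings with baselines that are central at Visit 2 and, on the natural reading, at Visit 15. Reading method is therefore fully confounded with change on drug. The shift in the mean equals the difference between methods, and its size and sign are unknown.

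The effect is confined to a descriptive summary of one component of the Extension primary safety endpoint. The documents do not show that Extension ECG results will be biased in a given direction, that the Core results are affected, or that a joined Core-to-Extension ECG trend is planned. The conclusion assumes that the SAP does not already specify a same-method baseline. Label: cheap improvement, low severity.

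**What to change.** In Appendix 5, Safety Analyses:

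- Compute Extension ECG change from baseline and outlier categories only from values read by the same method. Use the site (non-central) QTcF from the baseline visit already named there, where it can be retrieved from source.
- Where no same-method baseline exists, report absolute Extension values without change from the centrally read baseline.
- Present Core centrally read results separately and label the change of method.
- State how the Visit 15 ECG is read.

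The reference in Appendix 5 to Section 9.5, which requires central reading, and the bracket that removes it must be reconciled. So must the differing repeat-ECG triggers in Section 9.5.1.5.6, Table 5 footnote i and Table 9 footnote f.

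The cost is wording in Appendix 5 and the SAP, plus retrieval of site readings for Extension entrants. The baseline will be less precise than a central read, and some subjects, particularly those whose Visit 2 preceded Amendment 06, may have no same-method baseline. No added visit or tracing is needed.

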
Addition of optional tau PET longitudinal substudy for study-eligible subjects from select geographical sites in the US (based on the proximity to the tau PET ligand manufacturing sites) who have an amyloid positive study-specific PET scan and consent to participate in the optional amyloid PET longitudinal substudy. Tau PET scanning will be performed using a sponsor-supplied tau PET imaging agent, eg PI-2620.
	
To allow for longitudinal assessment of brain tau pathology by tau PET in a substudy. Abnormal aggregation of tau in the brain is a factor in many neurodegenerative diseases, including Alzheimer’s disease.
	
Synopsis
 
 • Objectives • Study Design • Assessments • Statistical Methods 
Section 5.3 Section 8.2 Figure 1 Section 9.1 Section 9.1.1 Section 9.1.1.1 Section 9.1.1.1.5 Section 9.1.2 Section 9.1.2.1 Section 9.2.4 Section 9.5.1.4.2 Table 3 Table 4 Section 9.7.1.1.4 Section 9.7.1.7.3

Revisions to Version 4.0

New version/date: Version 5.0/28 Jun 2017 (per Amendment 04)

Change	Rationale	Affected Protocol Sections
Added that the start of the open-label Extension Phase will require prior approval of an amendment from applicable Health Authorities	Added for consistency with Section 9.1.3.	Synopsis 
 • Study Design
Specified duration of the Prerandomization Phase and that randomization should occur no more than 10 days after completion of all screening assessments/procedures and confirmation of eligibility	Added for clarification	Synopsis 
 • Conduct of the Study Section 9.1.1 Section 9.1.2 Section 9.5.2.1 (Table 4)
Added that for any given subject, every effort should be made to ensure that the diagnosing clinician (responsible for the initial diagnosis and for disease staging) and the Clinical Dementia Rating (CDR) rater remain unchanged throughout the study.	Added to maximize consistency in diagnosis, disease staging and rating of the CDR.	Synopsis 
 • Conduct of the Study Section 9.1.1.1.1 Section 9.1.2.1 Section 9.5.1.3.1 Section 9.5.2.1 (Table 3 and Table 4)
Removed pharmacodynamic (PD) blood specimen collection from the Screening Period and stipulated that Baseline blood draws for PD assessment will be performed predose at Visit 2 (Randomization Phase) rather than during Screening.	Revised for clarification	Synopsis 
 • Conduct of the Study • Pharmacodynamic, Pharmacogenomic, and Other Biomarker Assessments Section 9.1.2 Section 9.1.2.1 Section 9.5.1.4.2 Section 9.5.2.1 (Table 4)
Specified that safety assessments of immune status will be performed throughout the study	Revised for clarification	Synopsis 
 • Conduct of the Study
Specified that the MMSE and CDR requirements are to be met at Screening	Revised for clarification	Synopsis 
 • Inclusion Criteria Section 9.3.1
Listed cerebrospinal fluid (CSF) amyloid beta (A β) (1-42) and tau:A β (1-42) ratio as examples of Alzheimer's disease (AD)	Revised for clarification, since since CSF assessment of brain amyloid pathology will also include other biomarkers	Synopsis 
 • Conduct of the Study • Inclusion Criteria • Pharmacodynamic,

Revisions to Version 4.0

New version/date: Version 5.0/28 Jun 2017 (per Amendment 04)

Change	Rationale	Affected Protocol Sections

biomarkers for brain amyloid pathology.
		
Pharmacogenomic, and Other Biomarker Assessments
 
 • Bioanalytical Methods 
Section 9.1.1.1 Section 9.1.1.1.5 Section 9.1.2 Section 9.1.2.1 Section 9.2.4 Section 9.3.1

Added that positron emission tomography (PET) scans performed at the Early Discontinuation (ED) Visit should only be performed if 6 months has elapsed since the prior PET scan.
	
Added to define a minimal interval between PET scans for the PET longitudinal substudy.
	
Synopsis
 
 • Conduct of the Core Study • Pharmacodynamic, Pharmacogenomic, and Other Biomarker Assessments 
Section 9.1.2 Section 9.1.2.1 Section 9.5.1.4.2 Section 9.5.2.1 (Table 4)

Specified that historical PET scans must have been positive for amyloid in order to be considered for eligibility purposes
	
Added for clarification
	
Synopsis
 
 • Inclusion Criteria • Pharmacodynamic, Pharmacogenomic, and Other Biomarker Assessments 
Section 9.3.1


Added that subjects must have the capacity to provide informed consent (as determined in accordance with applicable professional standards and local laws/regulations) to enroll in the study.
	
Added for clarification based upon feedback from Health Authority(ies)
	
Synopsis
 
 • Inclusion Criteria 
Section 9.3.1

Revisions to Version 4.0

New version/date: Version 5.0/28 Jun 2017 (per Amendment 04)

Change	Rationale	Affected Protocol Sections
Added that the study partner must be literate.	Added for clarification	Synopsis 
 • Inclusion Criteria Section 9.3.1
Specified that findings of “diffuse” white matter disease “as defined by a score of 3 on the age-related white matter changes score (Wahlund, et al., 2001)” on “central read” brain MRI findings at Screening are exclusionary. Clarified that evidence of multiple lacunar infarcts is exclusionary, regardless of region, whereas evidence of stroke is exclusionary when it involves a major vascular territory.	Added for clarification	Synopsis 
 • Exclusion Criteria Section 9.3.2 Section 10
Provided guidance for possible inclusion of subjects successfully treated for hepatitis C.	Added for clarification	Synopsis 
 • Exclusion Criteria Section 9.3.2
Specified that history of ophthalmic shingles or history of ocular herpes simplex virus infection are exclusionary, in addition to active infections of ophthalmic shingles or ocular herpes simplex virus.	Added for clarification	Synopsis 
 • Exclusion Criteria Section 9.3.2
Removed “ocular” inflammatory disease requiring immunosuppressive or immunomodulatory therapy from exclusion criteria	Ocular therapy is permitted.	Synopsis 
 • Exclusion Criteria • Concomitant Drug/Therapy Section 9.3.2 Section 9.4.7 Listing 2 of Appendix 2
Removed exclusion for significant abnormalities in laboratory tests or electrocardiogram (ECG) at Baseline assessment	Results from Baseline assessment will not be available at the Baseline Visit	Synopsis 
 • Exclusion Criteria Section 9.3.2

Revisions to Version 4.0

New version/date: Version 5.0/28 Jun 2017 (per Amendment 04)

Change	Rationale	Affected Protocol Sections
Clarified that the exclusion of subjects with a prolonged QTcF interval is based on the central read of the Screening ECG.	Added for clarification	Synopsis 
 Exclusion Criteria Section 9.3.2
Specified that “short-term” concomitant use of benzodiazepines is permitted as specified in the protocol	Added for clarification	Synopsis 
 Concomitant Drug/Therapy Section 9.4.7 Listings 5 and 6 of Appendix 2
Specified that repeat testing for subjects who develop Grade 2 or greater lymphocytopenia should be performed as soon as possible, with the repeat blood sample drawn no later than 5 calendar days from the date of the original test result.	Added for clarification	Synopsis 
 Safety Assessments Section 9.3.3
Updated text describing monitoring adverse events (AEs) that may signal drug abuse potential, physical withdrawal or dependence; specified that monitoring will include the Treatment Period and the first 4 weeks of the Follow-up Period	Added for clarification and alignment with current US Food and Drug Administration (FDA) Guidance for Industry for “Assessment for Abuse Potential for Drugs”	Synopsis 
 Safety Assessments Section 9.5.1.5.1 Section 9.5.2 (Table 4) Section 9.5.4.3.1 Section 10 Appendix 3
Added that of apolipoprotein E (ApoE) and N-acetyltransferase 2 (NAT2) genotype analyses will be performed using validated assays	Added for clarification	Synopsis 
 Bioanalytical Methods Section 9.5.1.4.2
Deleted Aβ(1-40) from biomarker endpoints and assessments	Analysis of the biomarker is no longer planned as a primary biomarker endpoint	Synopsis 
 Biomarker Endpoints Analyses for Biomarker Endpoints Section 9.5.1.4.2 Section 9.7.1.1.4 Section 9.7.1.7.3

Revisions to Version 4.0

New version/date: Version 5.0/28 Jun 2017 (per Amendment 04)

Change	Rationale	Affected Protocol Sections
Deleted instructions for subjects unable to read the informed consent, since illiteracy is an exclusion criterion	Removed for consistency with exclusion criterion 13	Section 5.3
Added that the Investigator shall reassess consent capacity at periodic intervals during the subject's involvement in the study and that the investigator must obtain subject assent and consent by the legal representative (in accordance with local laws and regulations) for subjects who lose the capacity to provide informed consent during the study.	Clarification based upon feedback from Health Authority(ies)	Section 5.3
Deleted reference to "in progress" status of the report for Study E2609-A001-003 and "preliminary" nature of data for Study E2609-A001-103	Clinical study reports are now final for both	Section 7.1
Specified that there are no contraceptive requirements for male subjects and that there is no requirement to follow partner pregnancies, based on in vivo nonclinical data..	Clarification based upon feedback from Health Authority(ies) and Ethics Committees	Section 7.1 Section 9.5.4.2
Provided duration of validity for screening Magnetic Resonance Imaging (MRI), amyloid PET and CSF assessments	Added for clarification regarding whether or not a rescreened subject needs to have these assessments repeated.	Section 9.1.1.1.4 Section 9.1.1.1.5
Specified that the 10 day period between completion of screening and randomization at Visit 2 starts with the reporting of the final screening assessment, which in most cases will be the confirmation of amyloid pathology	Added for clarification	Section 9.1.2 Section 9.5.2.1 (Table 3)
Provided a minimum recommended observation period following the first dose of study drug	Clarification based upon feedback	Section 9.1.2.1 Section 9.5.2.1 (Table 4)

Revisions to Version 4.0

New version/date: Version 5.0/28 Jun 2017 (per Amendment 04)

Change	Rationale	Affected Protocol Sections
Deleted reference to the non-amyloidogenic secretase pathway.	Alpha secretase is not evaluated in this study	Section 9.2.1
Deleted reference to whole brain analysis (the average of 5-6 cortical regions) and brain region analysis.	These analyses are not planned	Section 9.2.4
Deleted text indicating that a predetermined percentage of pharmacokinetic (PK) blood samples from placebo subjects will be analyzed.	PK analysis is no longer planned in subjects administered placebo.	Section 9.5.1.4.1
Added a table listing the planned pharmacodynamic, pharmacogenomic, and exploratory biomarker assessments	Added for clarification	Section 9.5.1.4.2 (Table 1)
Deleted assessment of beta-amyloid converting enzyme 1 (BACE1) levels as a planned analysis	A validated BACE1 assay has not been established; exploratory assessments may be performed	Section 9.5.1.4.2
Added that the blood sample collected at screening for determination of ApoE genotype is mandatory and that a subset of subjects will also be evaluated for NAT2 genotype.	Added for clarification	Synopsis 
 Pharmacodynamic, Pharmacogenomic, and Other Biomarker Assessments Section 9.5.1.4.2
Removed Tier 3 collection of blood sample for immunologic assessments, including isolation of PBMCs for storage at Screening	Collection and storage will begin at Visit 2	Section 9.5.2.1 (Table 3)
Added a separate column to the blood volume table for Visit 2 (Baseline) and revised specimen volume values	Added for clarification	Section 9.5.2.2 (Table 5)
The definition of a treatment-emergent adverse event (TEAE) was revised to specify emergence “on or after the start of study treatment”	Added for clarification	Section 9.7.1.8.2
Specified that only the test result	Added for clarification	Section 11.3

Revisions to Version 4.0

New version/date: Version 5.0/28 Jun 2017 (per Amendment 04)

Change	Rationale	Affected Protocol Sections
documentation from the urine dipstick test needs to be retained as source documentation.		
Itraconazole was added to the prohibited medications	Itraconazole is a strong inhibitor of carboxylesterase 2 (CES2) based on in vitro studies	Listing 1 of Appendix 2
Added a trade name for zolpidem	Added for clarification	Listings 6 of Appendix 2
Deleted “pharmacogenomics (PGx)” data from the description of individual subject data that may be returned to them or their physicians	Due to the blinded nature of the study design, this data will not be disclosed	Appendix 4.
Grammatical, typographical, and formatting changes were also made	Document quality	Throughout

Revisions to Version 3.0

New version/date: Version 4.0/04 April 2017 (per Amendment 03)

Change	Rationale	Affected Protocol Sections
Added that the start of the open-label Extension Phase will require a protocol amendment with prior approval from applicable Health Authorities.	Clarification based upon feedback from Health Authority(ies)	Synopsis 
 • Extension Phase Section 9.1.3
Added that the end of the study for the double-blind Randomization Phase will be the date of the last study visit (Visit 15) for the last subject in the double-blind Randomization Phase.	Clarification based upon feedback from Health Authority(ies)	Synopsis 
 • Study Design Section 9.1.4 (new)
Extended the requirement of compliance with local standard of care for concomitant use of acetylcholinesterase inhibitor (AChEI) or memantine for symptomatic treatment of Alzheimer's disease (AD) to include initiation or changing dose of AChEI or memantine during the study.	Clarification based upon feedback from Health Authority(ies)	Synopsis 
 • Concomitant Drug/Therapy Section 9.4.7
Revised description of blood/CSF collection and assay for pharmacodynamic (PD) and exploratory biomarkers.	Added for clarification	Synopsis 
 • Pharmacodynamic, Pharmacogenomic, and Other Biomarker Assessments Section 9.5.1.4.1 Section 9.5.1.4.2 Section 9.5.2.1 (Table 3 and Table 4)
Specified that peripheral blood mononuclear cells (PBMCs) will be stored for testing as required.	Added for clarification	Section 9.1.1.1.3 Section 9.1.2.1
Revised text to include cerebrospinal fluid (CSF) for description of exploratory biomarkers	Corrected missing information	Section 9.2.4

Revisions to Version 3.0

New version/date: Version 4.0/04 April 2017 (per Amendment 03)

Change	Rationale	Affected Protocol Sections
Revised text for amyloid CSF sampling to note that 2 methods are available rather than required	Revised for clarification	Section 9.5.1.3.3 Section 9.5.1.5 Section 9.5.1.5.3 (Table 22) Section 9.5.2.1 (Table 3 and Table 4)
Specified definition of moderate or severe hepatic impairment	Clarification based upon feedback from Health Authority(ies)	Section 9.3.3
Added that subjects who develop seizures will be discontinued from study drug.	Clarification based upon feedback from Health Authority(ies)	Section 9.3.3

Defined severe infection as follows: sepsis; deep tissue (invasive) infection; any infection requiring intravenous (IV) antibiotics; any infection requiring hospitalization (if outpatient at onset); any infection leading to need for oxygen, pressors or fluids to support blood pressure, or intubation; any infection that requires major surgical intervention; pseudomembranous colitis due to C. difficile; typhlitis; osteomyelitis; and meningitis.
 
Added that for subjects who develop severe infections, study drug administration should be interrupted for a maximum period of 4 weeks. Subjects who recover from severe infections within 4 weeks may resume treatment if deemed appropriate by the investigator after consultation with Medical Monitor. Subjects should permanently discontinue study drug if the severe infection has not resolved within 4 weeks.
	Clarification based upon feedback from Health Authority(ies)	Section 9.3.3 Section 9.5.1.5.1

Revisions to Version 3.0

New version/date: Version 4.0/04 April 2017 (per Amendment 03)

Change	Rationale	Affected Protocol Sections
Revised study drug interruption and discontinuation criteria for skin rash and herpes infections. Added instructions for drug consultation with the Medical Monitor and potential rechallenge.	Clarification based upon feedback from Health Authority(ies)	Section 9.3.3 Section 9.5.1.5.5
Revised dose selection to note that PK/PD modeling indicates elenbecestat (E2609) 50 mg per day results in reduction of median CSF A β by approximately 70%.	Clarification based upon feedback from Health Authority(ies)	Section 9.4.4
Corrected the description for calculating the immediate memory score on the Alzheimer’s Disease Assessment Scale - cognitive subscale (ADAS-cog ₁₄)	Corrected error	Section 9.5.1.3.1
Added measurement of prothrombin time, international normalized ratio (INR; derived from prothrombin time), and activated partial thromboplastin time (aPTT) to each study visit.	Added to support evaluation of hepatic function at each visit	Section 9.5.1.5.3 (Table 22) Section 9.5.2.1 (Table 3 and Table 4)
Added clarification of the clinical assessment of suicidal thinking and behavior to be conducted at visits that do not include administration of the Columbia Suicide Severity Rating Scale (C-SSRS); which includes asking the subject “Since the last time we spoke have you had any thoughts or attempts to end your life by suicide?” and asking their study partner “Since the last time we spoke has the subject shared any thoughts or are you aware of attempts at suicide?”.	Clarification based upon feedback from Health Authority(ies)	Section 9.5.1.5.9

Revisions to Version 3.0

New version/date: Version 4.0/04 April 2017 (per Amendment 03)

Change	Rationale	Affected Protocol Sections
Corrected number of time points and blood volume per collection for pharmacokinetic analysis during the treatment and follow-up periods; added specimen collection for coagulation; added clarification that the volumes are estimates and may vary based on local regulations.	Corrected error	Section 9.5.2.2 and Table 5
Grammatical, typographical, and formatting changes were also made	Document quality	Throughout

Revisions to Version 2.0

New version/date: Version 3.0/06 Feb 2017 (per Amendment 02)

Change	Rationale	Affected Protocol Sections

An editorial revision was made to add “elenbecestat”, the proposed International Nonproprietary Name (pINN) for “E2609”; grammatical, typographical, and formatting changes were also made
	
The revision was made to provide consistency for current and future elenbecestat (E2609) clinical development documents.
	
All sections of the protocol that previously included “E2609” or required editorial revision

Revised the first exploratory objective to the following: To explore the relationship between elenbecestat (E2609) exposure/PD (in CSF, plasma) with efficacy and safety endpoints (eg, immune function) as deemed appropriate
	
To include exploration of the PD relationship of study drug to PK, efficacy, and immune function
	
Synopsis
 
 • Exploratory Objectives • Study Design • Pharmacodynamic, Pharmacogenomic, and Other Biomarker Assessments • Bioanalytical Methods 
Section 8.3 Section 9.2.4

